8.4 Recording and Reporting of Anticipated Effects

At each contact with the participant, the investigator will seek information on the occurrence of any known (anticipated) effects of the intervention by specific questioning and, as appropriate, by examination (see Attachment 7, Adverse Event Reporting). Information on all anticipated effects will be recorded immediately in the source document. All clearly related signs, symptoms, and abnormal diagnostic procedure results will be recorded in the source document, grouped under one diagnosis.

All anticipated effects occurring during the study period will be reported to the appropriate research personnel involved in the participants' intervention programs. The clinical course of each event will be followed until resolution, stabilization, or until it has been determined that the study treatment or participation is not the cause. Any effects that are still ongoing at the end of the study period will be followed up to determine the final outcome. Any effects that occur after the study period will be recorded and reported promptly. The minimum initial information to be captured in the subject's source document concerning the anticipated effects are listed in section 8.2.

Documented cases of mild side effects related to delivery of ACS which occasionally occurred include: erythema (skin reddening), skin tingling, skin itching, skin burning sensation, sensation of warmth at site of electrode placement, nausea, diffuse or migraine-like headache, facial muscle twitching, blurred vision, short-lived localized head pain or pressure, weak headache, forgetfulness, difficulty concentrating, change in mood, dizziness, general fatigue, sleeping difficulties (temporary), spontaneous phosphenes (independent of stimulation), blood pressure fluctuation, and difficulty breathing (103, 106).

Participants may experience double vision and difficulty in near vision tasks (e.g., reading), which is common, as an effect of dilating eye drops used during the clinical vision evaluation. Additionally, dilating eye drops may cause: redness of the eye, tearing or stinging of the eye, feeling faint or dizzy, and/or sensitivity to light. As it is standard of care, it is recommended that participants arrange for someone to

CONFIDENTIAL

This material is the property of the NYU School of Medicine and Langone Medical Center. Do not disclose or use except as authorized in writing by the study sponsor

assist them in their transportation after the study visit. It is also recommended participants wear sunglasses when they go outside or into a brightly lit room. The effects of these dilating drops will disappear within 3-4 hours after they are instilled in the eye. Pupillary dilation may cause an increase in eye pressure or the possibility of an angle-closure event, which happens in a rare configuration of the eyes. There is a low risk that the instrument used to check participants' eye pressures (standard of care) might cause a scratch on the cornea. All participants will be examined clinically before dilating drops are instilled to identify eyes at risk, in which no dilation drops will be used. If either of these risks should occur, the participant will be treated immediately at no cost.

There is minimal risk of eye infection to participants from the ophthalmic testing procedures. To reduce the risk of eye infection, all exposed surfaces near the eye, as well as chin rest and forehead rest of the instruments, will be cleaned with alcohol before participants are examined per standard practice.

Some research subjects have reported mild discomfort with MRI scans. MRI uses a strong magnetic field to create images of the body. Because of the strong magnetic field, there are risks. One possible risk is burns to the skin. There is an increased risk of burns from devices that conduct electrical energy. These devices can include metallic objects or skin tattoos. These devices can be either in or on the patient in order for a skin burn to occur. The FDA has found that 70% of all who reported injuries from MRIs were burns to the skin. To reduce this risk, all participants who are scanned in this study must complete thorough screening to ensure that no conductive materials are present in or on the participant's body. Additionally, the power limits of the magnet will be adjusted as necessary. Another possible risk is that a metal object could be pulled into the scanner and hit the participant. To reduce this risk, everyone near the magnet will remove all metal from his/her clothing or pockets when in the scanning environment. Participants will be carefully screened to ensure no metal objects enter the magnetic field and they will be asked to place all metallic and magnetic objects in their possession (e.g., keys, jewelry, credit cards) in a secure location outside the magnet room.

The magnetic fields, at the strengths used, are felt to be without harm and the MRI scanning procedures fall within the FDA guidelines for radiofrequency electromagnetic field exposure. It is felt these are safe levels and less hazardous than a comparable x-ray computed tomography examination. Exceptions include if a person has electrically, magnetically, or mechanically activated implants (such as cardiac pacemaker), or clips on blood vessels in their brain, or other metallic objects in their body such as shrapnel, bullets, buckshot, or metal fragments. Therefore, participants will be carefully screened for previous exposure to metallic fragments or to implanted devices.

If participants are prone to claustrophobia, they will be asked to notify the researcher in charge of the scan, who will discontinue the scan upon the participant's request. The MRI scanner makes loud knocking or beeping sounds during imaging; earplugs will be provided to help reduce this noise. Due to the rapid rate of change of the magnetic gradients during imaging, peripheral nerve stimulation is possible. If this happens, participants may feel creeping or tingling sensations, typically along their arms or lower back. Dizziness and nausea may occur if the participants move their head in the bore of the magnet. Finally, rarely there may be some heating from the radio frequency coils, the cables to the coils, response and physiological monitoring devices. If at any time participants feel discomfort, they will be instructed to contact the operator immediately. They will also be instructed in how to use an emergency handheld device to inform the operator if they wish to immediately stop scanning and be removed from the magnet.

8.5 Unmasking Procedures

Allocation to group (unmasking) will be revealed once all participants complete the study procedures. In the event when the safety of the participant is in question, per protocol participants will be assessed by the physicians involved in this study and care directed and/or referred accordingly. Given the consistent reports for safety and tolerability of rtACS across several clinical trials, we don't anticipate the occurrence of any adverse events or adverse effects that are the direct consequence of rtACS; therefore, there is likely not a justifiable need for unmasking to occur prior to the study's end.

CONFIDENTIAL

This material is the property of the NYU School of Medicine and Langone Medical Center. Do not disclose or use except as authorized in writing by the study sponsor

At the study's end, the staff personnel who managed the allocation concealment and randomization processes will reveal the allocation (database) to the study research team involved in any subsequent communication with participants. Participants will be informed of their group randomization at the conclusion of their participation in the study via face-to-face or phone conversation with research personnel, documented in the participant's source document.

In the unlikely event when unmasking is deemed to occur related to managing an adverse event, the unmasking will be reported with the adverse event. In the unlikely event when unmasking is not associated with an adverse event, unmasking will be reported to the research team in an immediate and timely manner.

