5.3 Method for Assigning Subjects to Treatment Groups

For the randomization scheme, participants will be randomized (1:1 ratio) to the rtACS and sham stimulation groups using blocked randomization stratified by Centers (to determine any differences between the Centers). Random varying block sizes will be used to balance group allocation and minimize the risk of unmasking group assignment, and a randomization table will be computer generated accordingly. A statistician will generate a randomization table and a research staff member indirectly involved in the conduct of this study will conduct the process of allocation. Participants will be assigned in the order that they are enrolled. The randomization and allocation concealment will be uploaded to a secure database.

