9.5 Electronic Medical Record and Release of Study-Related Information

In compliance with the 21st Century Cures Act, some research-related information in subjects' Electronic Medical Records will not be immediately available in order to protect the randomization integrity of the research. The suppressed information will be accessible to subjects once the study is concluded. The information to be suppressed includes: visual field results, OCT imaging, and ophthalmic report.

10 Study Monitoring, Auditing, and Inspecting

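### Section 8.5 gives two times for telling participants their arm: after everyone has finished, and at the end of each participant's own participation

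*Combined protocol and SAP*

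**What the plan says.** Section 8.5 makes four statements about when arms become known.

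- General rule: "Allocation to group (unmasking) will be revealed once all participants complete the study procedures".
- Early unmasking: given the safety record, "there is likely not a justifiable need for unmasking to occur prior to" the end of the study.
- Release of codes: at the study's end, the staff who managed allocation "reveal the allocation (database) to the study research team involved in any subsequent communication with participants".
- Telling participants: "Participants will be informed of their group randomization at the conclusion of their participation in the study". The same sentence has research staff do this in person or by telephone and note it in the participant's source document.

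A closing paragraph covers unmasking linked to an adverse event, and unmasking for other reasons.

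Related provisions lie elsewhere. In section 5.3, "The randomization and allocation concealment will be uploaded to a secure database" and "Random varying block sizes will be used to balance group allocation and minimize the risk of unmasking group assignment". Sections 5.7 and 6 have the stimulator set up by staff who take no part in data collection or analysis. Section 3.1 names participants and interventionists as the masked parties. Section 9.5 withholds visual field results, OCT imaging and the ophthalmic report, and there "The suppressed information will be accessible to subjects once the study is concluded"; that rule concerns test results, not arms.

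**The concern.** The general rule is tied to the whole study. The sentence on telling participants is tied, by its plain words, to the individual. With staggered enrolment these are different dates. The participant-level sentence is also the only one that deals specifically with informing participants, so it is where staff would look when someone who has finished asks which arm they were in.

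If it were followed, the main risk would fall on participants enrolled later:

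- Research personnel would learn arms and write them in source documents while the trial was still running. Under section 6, baseline, post-intervention and follow-up assessments for all participants take place at one centre.
- Assessors are not named as masked. What keeps arms from them is the separation of set-up staff and the withholding of codes until study end, so the release rule carries real weight.
- Section 11 has the personnel who administer assessments also obtain consent, and nothing separates them from those who would disclose arms. Known earlier arms in a blocked sequence make the next one easier to guess, which varying block sizes are meant to prevent.
- Some outcomes leave room for influence: LIFE-H is interviewer-administered (section 3.2.2.1), and section 4.1 itself calls the visual field test subjective. The OCT measures, which the device software produces automatically (section 3.2.1.1), are less exposed.

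A participant's main outcomes through follow-up are collected before disclosure under either reading. There is one exception. Section 6.1.2 has the PSQI collected by contacting people who are already through follow-up, and under the literal sentence they could answer knowing their arm.

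**Working it through.** **The texts side by side.** The general rule fixes the time at completion by all participants. The release of codes is fixed at the study's end. The sentence on telling participants is fixed at the conclusion of *their* participation. No section defines the last as study end or says that one sentence overrides another.

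**Do the two times differ in practice?** Inputs:

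- 16 participants, with recruitment planned from April 2017 to December 2020 (section 3.1, Table 1). The days of the month are not given; 1 April and 31 December are assumed.
- Baseline within five business days before sessions, about 1 week (section 6.1); sessions over 2 weeks (section 6.2); follow-up 4 weeks after the last session (section 6.4).

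Length of one participation: 1 + 2 + 4 = about 7 weeks.

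Recruitment window: 1 April 2017 to 31 December 2020 = 1,370 days; 1,370 / 7 = 195.7 weeks.

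Even spacing: 195.7 / 15 intervals = 13.0 weeks between enrolments. The 15th participant finishes 7 weeks after enrolling, about 6 weeks before the 16th enrols. So all 15 could have been told by then. This holds whenever the spacing exceeds 7 weeks, that is, for any window longer than 15 × 7 = 105 weeks, including recruitment slower than planned.

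Random arrivals: if 16 enrolments fall independently and uniformly over a window of T weeks, the expected number finished before the last enrols is close to 15 × [1 − 7 × 16 / (15 × T)] = 15 − 112 / T. A simulation of 20,000 runs gave the same means.

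| Recruitment window | Even spacing | Random arrivals, mean |
|---|---|---|
| 195.7 weeks (planned) | 15 of 15 | 15 − 0.57 = 14.4 |
| 156 weeks | 15 of 15 | 15 − 0.72 = 14.3 |
| 104 weeks | 14 of 15 | 15 − 1.08 = 13.9 |
| 52 weeks | 13 of 15 | 15 − 2.15 = 12.8 |

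The simulated 5th to 95th percentiles were 13–15 for the planned window and 10–15 for 52 weeks. The last three rows are faster than planned; they show that the count stays high even with much quicker recruitment. Under the study-level rule the count is 0 in every row.

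**Longest wait under the study-level rule.** The time from the first participant's completion to the last's equals the gap between their enrolments: 1,370 / 365.25 = 3.75 years.

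How often a next arm could be guessed is not calculated, because the documents give neither the block sizes nor the split between centres.

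**The case against.** The strongest reply is that section 8.5 already works as a sequence. It opens with the study-level rule, then releases the codes at the study's end to those who will communicate with participants, and only then describes that communication. The people who would do the telling do not hold the codes earlier, so telling anyone sooner would also breach the sentence just before. On this view the participant-level words are loose drafting. The harm would need several departures in a row: early release from the secure database, arms reaching assessors, and assessors making use of them.

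Much of this stands. Study end is the better-supported reading, and the harm is conditional. What it does not do is remove the literal conflict. Study end has to be inferred from sentence order, while the sentence that addresses the matter directly states a different time. A masking rule that staff must apply should not rest on inference.

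A reader might go further and infer that the plan unmasks participants one by one throughout recruitment, or that its results would be biased. The documents support neither. The rest of section 8.5 points the other way, and nothing shows that early disclosure happened or was intended.

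**Conclusion.** Wrong as written, of minor severity: section 8.5 contradicts itself on when participants learn their arm. The contradiction rests on the wording alone and needs no assumption.

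Its possible reach does depend on assumptions: that the participant-level sentence is followed, that the planned dates hold, and that one participation lasts about 7 weeks. On those terms essentially all 15 earlier participants could be told before the last enrols, and about 13 of 15 with recruitment compressed to 52 weeks. These counts show how far apart the two times are; they do not show that early disclosure is likely. If arms never reached those who enrol or assess, later participants' data would be unaffected. The PSQI exposure applies only where that questionnaire is collected after disclosure. No bias in any outcome is estimated.

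**What to change.** In section 8.5, give the sentence on telling participants the section's own trigger and keep the adverse-event route open. For example: *Except where unmasking occurs as described below, participants will be informed of their group once all participants complete the study procedures*, followed by the existing words on face-to-face or phone contact and source documentation. Leave the closing paragraph on unmasking unchanged. Using the opening rule's trigger, rather than a last follow-up visit, avoids introducing a third time point; a few words confirming that late PSQI contacts count as study procedures would settle that case too.

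The cost is one sentence. The drawback is for participants: on the planned dates the earliest would wait up to about 3.75 years to learn their arm, and longer if recruitment ran past December 2020.

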8.6 Medical Monitoring

It is the responsibility of the PI to oversee the safety of the study at his/her site. This safety monitoring will include careful assessment and appropriate reporting of adverse events as noted above, as well as the construction and implementation of a site data and safety-monitoring plan (see section 9). Medical monitoring will include a regular assessment of the number and type of adverse events. The PI and lead research investigators and personnel will be ultimately responsible for the data safety monitoring of the overall study and will meet bimonthly to monitor data, recruitment, retention, confidentiality, and adherence to the study protocol.

9 Data Handling and Record Keeping

9.1 Confidentiality

Information about study participants will be kept confidential and managed according to the requirements of HIPAA (1996). Those regulations require a signed subject authorization informing the subject of the following:

- What protected health information (PHI) will be collected from subjects in this study
- Who will have access to that information and why
- Who will use or disclose that information
- The rights of a research subject to revoke their authorization for use of their PHI.

In the event that a participant revokes authorization to collect or use PHI, the investigator, by regulation, retains the ability to use all information collected prior to the revocation of subject authorization.

All medical information collected from participants and documentation related to their participation in the study will be kept in a locked cabinet designated for research conducted at NYU Langone Eye Center during the conduct of the study. Unique patient identifiers will be used to label all data; a password-protected linking file will be accessible to/managed by the study PI and Co-PI. Strict standards of confidentiality will be upheld at all times.

9.2 Source Documents

Source data is all information, original records of clinical findings, observations, or other activities in a clinical trial necessary for the reconstruction and evaluation of the study. Source data will be kept in participant files that will be physically located in a locked filing cabinet in a locked office at NYU Langone Eye Center during the conduct of the study. Research data will be entered online through the NYU and HIPAA compliant database, designed specifically for this study. An anonymous database number will be assigned to each participant and will be used for both the data entry sheets and the patient follow-up sheets. Data collected using the Linking File Form (see Attachment 6), which includes the participant's name and study ID number, will be stored separately from participants' data files in a password protected electronic file. Access to this data will be restricted to study personnel only. The assigned ID will code participant data and identifying information will not be presented or published to maintain participant privacy and confidentiality.

CONFIDENTIAL

This material is the property of the NYU School of Medicine and Langone Medical Center. Do not disclose or use except as authorized in writing by the study sponsor

9.3 Case Report Forms

The study Case Report Form (see Attachment 6) is the primary data collection instrument for the study. All data requested on the Case Report Form will be recorded. All missing data will be explained. If a space on the Case Report Form is left blank because the procedure was not done or the question was not asked, write "N/D". If the item is not applicable to the individual case, write "N/A". All entries will be printed legibly in black ink. If any entry error has been made, to correct such an error, a single straight line will be drawn through the incorrect entry and the correct data entered above it. All such changes will be initialed and dated. For clarification of illegible or uncertain entries, print the clarification above the item, then initial and date it.

9.4 Records Retention

A list of all persons authorized to perform study procedures will be maintained in the Regulatory Binder. All study related essential documentation will also be kept in the Regulatory Binder. The assigned study staff will maintain participants' study files and source documentation. Study files will be kept locked in the research offices. Following completion or termination of the study, all study documents will be kept for a minimum of 2 years as required by the IRB.

9.5 Electronic Medical Record and Release of Study-Related Information

In compliance with the 21st Century Cures Act, some research-related information in subjects' Electronic Medical Records will not be immediately available in order to protect the randomization integrity of the research. The suppressed information will be accessible to subjects once the study is concluded. The information to be suppressed includes: visual field results, OCT imaging, and ophthalmic report.

10 Study Monitoring, Auditing, and Inspecting

10.1 Study Data and Safety Monitoring Plan

We will utilize operating procedures for reviewing patient safety data and source data generated from this study. This will include routine monitoring according to the Data and Safety Monitoring Plan (see Attachment 8), allowing for adequate time and space for such monitoring activities and that the monitor or other compliance or quality assurance reviewer is given access to all the above noted study-related documents and study related facilities. The following aspects will be specifically monitored: enrollment and retention, data collection, confidentiality, multi-centers, breaches from the study protocol, and any adverse event.

Data and safety monitoring will include monthly meetings between the PI, research investigators, study coordinators, and pertinent study research personnel as necessary. The Data and Safety Monitoring Plan encompasses the research-related activities as they apply to recruitment and screening procedures conducted at New York Eye and Ear Infirmary of Mount Sinai. At these meetings, the research team will review the clinical ratings, assessments, clinical course, and study processes for each active participant as they apply to each Center. Specific attention will be given to data quality and timeliness, HIPAA compliance, safe storage of data, and data backup of electronic source data. Attention will also be given to participant recruitment, accrual and retention, participant risk versus benefit, adverse events, and other factors that can affect study outcome, including scientific or therapeutic developments that may have an impact on the safety of the participants or the ethics of the study.

There are no predetermined stopping rules for this pilot study. As needed, a yearly report will be submitted to the IRB during the renewal as to the frequency of monitoring and a summary report addressing any recommendations to adjust the risk/benefit ratio, participant privacy, or confidentiality procedures.

All data will be shared with previous PI [name] for study analysis.

CONFIDENTIAL

This material is the property of the NYU School of Medicine and Langone Medical Center. Do not disclose or use except as authorized in writing by the study sponsor

